8.2.1.2 Secondary and exploratory endpoints

8.2.1.2.1 Secondary Endpoints

- PFS assessed according to RANO criteria and assessed by IRC. In addition to the Hazard Ratio, the following parameters will be computed in each arm: median PFS, probability of progression or death at 6 months (PFS6), probability of progression or death at 1 year (PFS12).
- The OS analysis will be performed in the subgroup with EGFRvIII mutation.
- Objective response rate (ORR) assessed by IRC will be computed in each arm.

8.2.1.2.2 Exploratory Endpoints

- The PFS analysis will be performed in the subgroup with EGFRvIII mutation.
- Best overall response rate (BOR), complete response rate (CRR), duration of response (DR) assessed by IRC will be computed in each arm.
- Neurological Deterioration Free Survival (NDFS), in addition to the Hazard Ratio, the following parameters will be computed in each arm: median NDFS, probability of NDFS at 6 months (NDFS6), probability of survival at 1 year (NDFS12).
- Frequencies and percentages of worst Adverse Event (AEs) or Laboratory Event grades and grade 3/4 per AE term and category as measured by CTCAEs Version 4.0 criteria.
- Quality of Life will be assessed and analyzed according to the methodology described in chapter 10.
- Use of steroids will be analyzed (but not exclusively) with the methodology developed by Vredenburgh et al. (Ref. 39). Schedule of collection of steroids data is detailed in chapter 6.

8.2.2 Analysis populations

- ◆ Intention-to-treat population (ITT): All randomized patients will be analyzed in the arm they were allocated by randomization.
- ◆ Per protocol population (PP): All patients who are eligible and have received at least one dose of the study drug (i.e. one dose of lomustine or TMZ (arm 3), of ABT-414 (arm 2) and of TMZ and ABT-414 (arm 1)). Patients will be classified and analyzed in the arm they were assigned at the time of randomization.
- ◆ Safety population (SP): All randomized patients who have received at least one dose of the study drug (i.e. one dose of lomustine or TMZ (arm 3), of ABT-414 (arm 2) and of TMZ and ABT-414 (arm 1)). Patients will be classified according to treatment received.

A patient will be considered to be eligible if he/she did not have any deviation from the patient entry criteria listed in chapter 3 of the protocol. Potential eligibility problems will be assessed by the Clinical Research Physician at time of medical review.

8.2.3 Statistical methods

8.2.3.1 Overall Survival

In the ITT:

OS will be compared between arm 1 versus arm 3 and/or arm 2 versus arm 3 when 170 deaths (118 per comparison) are observed.

Differences between the treatment groups in OS will be assessed by a Logrank test stratified by the randomization stratification factors, testing the null hypotheses (H1: Arm 1 is not superior to Arm 3 in OS; H2: Arm 2 is not superior to Arm 3 in OS, respectively). The hazard ratios of the two treatment arms over the control arm will be calculated by Cox's proportional hazards model (score test) stratified by randomization stratification factors.

The OS probability at 12 months (OS12), at 2 years (OS24) and the median OS (mOS) will be estimated from the Kaplan-Meier OS curve. Two-sided 95% CI will be computed based on the Greenwood's formula. For the median the Reflected Method will provide two-sided 95% CI.

8.2.3.2 Progression Free Survival

In the ITT (RANO criteria assessed by IRC):

Differences between the treatment groups in PFS will be assessed by a Logrank test stratified by the randomization stratification factors, testing the null hypotheses (H1a: Arm 1 is not superior to Arm 3 in PFS; H2a: Arm 2 is not superior to Arm 3 in PFS, respectively). The hazard ratios of the two treatment arms over the control arm will be calculated by Cox's proportional hazards model (score test) stratified by randomization stratification factors.

The PFS probability at 6 months (PFS6), at 12 months (PFS12) and the median PFS (mPFS) will be estimated from the Kaplan-Meier PFS curves. Two-sided 95% CI will be computed based on the Greenwood's formula. For the median the Reflected Method will provide two-sided 95% CI.

8.2.3.3 Radiological response

In the ITT (RANO criteria assessed by IRC):

The best overall response will be presented in contingency table with frequencies and percentages. The objective response (ORR: CR/PR) and complete response rates will be reported with exact (binomial) two-sided 95% CI. The medians of objective (PR/CR) and complete (CR) response duration will be estimated from the Kaplan-Meier curves. The Reflected Method will provide two-sided 95% CI.

8.2.3.4 OS and PFS in patients with EGFRvIII mutation

In the ITT (for PFS, RANO criteria assessed by IRC):

OS and PFS analyses will be performed in the subgroup of patients with EGFRvIII mutation at final analysis. The same methodology as for analyses in the whole cohort will be applied (see sections [8.2.3.1](#), [8.2.3.2](#)).

8.2.3.5 Neurological Deterioration Free Survival

In the ITT:

Differences between the treatment groups in NDFS will be assessed by a Logrank test stratified by the randomization stratification factors, testing the null hypotheses (H0: NDFS of the 2 treatment arms equal to that of control arm; Arm 1 vs. Arm 3 and Arm 2 vs. Arm 3, respectively). The hazard ratios of the two treatment arms over the control arm will be calculated by Cox's proportional hazards model (score test) stratified by randomization stratification factors.

The NDFS probability at 6 months (NDFS6), at 12 months (NDFS12) and the median NDFS (mNDFS) will be estimated from the Kaplan-Meier NDFS curve. Two-sided 95% CI will be computed based on the Greenwood's formula. For the median the Reflected Method will provide two-sided 95% CI.

8.2.3.6 Global strategy to control type I error for efficacy endpoints

To meet global regulatory requirements, a multiple testing strategy for the following ordered endpoints will be implemented to control the family-wise type I error (alpha) for comparisons of Arm 1 (ABT-414 + TMZ) versus Arm 3 (TMZ/lomustine) and Arm 2 (ABT-414 alone) versus Arm 3 with respect to overall survival (OS) and the pre-defined secondary efficacy endpoints, namely progression-free survival (PFS), objective response rate (ORR), and OS for patients with EGFR vIII mutation.

The following null hypotheses are considered:

H1: Arm 1 is not superior to Arm 3 in OS.

H2: Arm 2 is not superior to Arm 3 in OS.

H1a: Arm 1 is not superior to Arm 3 in PFS.

H2a: Arm 2 is not superior to Arm 3 in PFS.

H1b: Arm 1 is not superior to Arm 3 in ORR.

H2b: Arm 2 is not superior to Arm 3 in ORR.

H1c: Arm 1 is not superior to Arm 3 in OS among EGFR vIII mutated patients.

H2c: Arm 2 is not superior to Arm 3 in OS among EGFR vIII mutated patients.

[figure not shown]
To maintain the overall type I error control for the study, the following null hypotheses will be tested in a fixed sequence of {H1, H2, H1a, H2a, H1b, H2b, H1c, H2c} in order at a 1-sided 2.5% level of significance. Hypothesis H1 will be tested first at a 1-sided 2.5% level. No further tests will be performed if H1 is not

rejected. Each hypothesis will be tested in order specified above if H1 and all preceding hypotheses show statistically significant results at the 1-sided 2.5% level of significance. Otherwise testing in the fixed sequence will stop.

All other endpoints, e.g., PFS in EGFRvIII mutated, global health/QoL status (GHQs), and neurological disease-free survival (NDFS) are considered exploratory and will be tested at a 2-sided 5% level of significance.

Arm 1 vs. Arm 3

Arm 2 vs. Arm 3

8.2.3.7 Safety and tolerability

In the SP:

The safety and tolerability analyses will be presented for the whole study duration. Severe grades (3/4) which did not resolve after treatment discontinuation or emerged during follow-up will be identified and listed. All forms up to the last safety assessment before progression or start of further anti-tumoral therapy will be used. There will be no formal comparison of safety endpoints. No p-value and confidence intervals will be carried out. Baseline laboratory and AE grades will not be accounted for in whole study duration safety analyses.

Laboratory and AE events occurring in patients who did not start their allocated treatment (ie excluded from SP) will be reported separately.

8.2.3.7.1 Hematological parameters

The worst value of each hematological category will be identified and graded for each patient. Frequencies and percentages of each category will be tabulated per arm. A table with grade 3/4 frequencies and percentages will be provided.

8.2.3.7.2 Biochemical parameters

The worst value of each biochemical category will be identified and graded for each patient. Frequencies and percentages of each category will be tabulated. A table with grade 3/4 frequencies and percentages will be provided.

8.2.3.7.3 All AEs

The worst grade of each AE item will be identified for each patient. Frequencies and percentages of each CTCAE term will be tabulated grouped by System Organ Class (SOC). Tables with all grades and grade 3/4 frequencies and percentages will be provided.

8.2.3.7.4 SAEs

After reconciliation with the SAEs listing extracted from the pharmacovigilance database, the worst grade of each SAE item will be identified for each patient and will be considered for the analysis. Frequencies and percentages of each CTCAE term will be tabulated grouped by SOC. Tables with all grades and grade 3/4 frequencies and percentages will be provided.

8.2.3.7.5 Related AEs

The worst grade of each related AE item will be identified for each patient. Frequencies and percentages of each CTCAE term will be tabulated grouped by SOC. Tables with all grades and grade 3/4 frequencies and percentages will be provided.

8.2.4 Pre-planned sensitivity or exploratory analyses

In case more than 10% are excluded from the PP, OS analysis (both comparisons) will be performed in the PP population at two-sided alpha 5%.

In the ITT, for OS, PFS, tumor response, NDFS treatment effect will be assessed in the following subgroups:

- Timing of relapse: < 16 weeks and ≥ 16 weeks after the first day of the last TMZ cycle;
- MGMT promoter methylation status: methylated and unmethylated;
- EGFR pathway abnormalities: abnormal and normal.

To assess the predictive value of the above three factors for OS, PFS, NDFS, the score interaction test will be computed by fitting a Cox regression model including treatment, factor and interaction term (treatment X factor). Forest plots will be displayed. KM curves comparing treatments will be presented in each subgroup.

To assess factor univariate prognostic value, the score test will be computed by fitting a Cox model including the factor in each arm (control and treatments). KM curves by factor stratum will be displayed.

For treatment comparison and prognostic value assessment, an exploratory two-sided significance of 5% will apply. For each interaction test, a significance of 10% will apply.

Treatment comparisons in the ITT population and above mentioned other sensitivity analyses will also be performed with PFS assessed by local investigators with the same calculation methods than for PFS assessed by IRC. Other exploratory analyses may be performed based on other subsets of patients. The results of these exploratory analyses may not serve as a basis for drawing conclusions concerning protocol efficacy, but rather as hypothesis generating and the rationale for additional subset analyses should be clearly documented.

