In a U87 model expressing EGFRvIII, the activity of RT/TMZ was significantly increased when ABT-414 was co-administered, whereas ABT-414 plus TMZ was more effective compared to ABT-414 with RT. The responses observed in the ongoing phase I study were on patients receiving both TMZ and ABT-414. This leaves the possibility open that TMZ may add to the activity of ABT-414. In case of favorable results in the combination arm ABT-414/TMZ it will be possible that this is in part caused by activity of TMZ. This brings the need to design phase II studies in a way this can be addressed. It is however not justifiable to have a control arm with TMZ in a phase II study on recurrent glioblastoma, as many glioblastoma patients are relapsing during or shortly after TMZ chemotherapy. In these patients, retreatment with temozolomide is not rational, and another comparator is needed. Still, having TMZ treated patients in the control arm will allow some further analysis of a potential TMZ contribution to the outcome. As illustrated above, for selected glioblastoma patients (in particular those relapsing more than three months after the end of adjuvant TMZ adjuvant chemotherapy) TMZ re-treatment is an option. Therefore, the treatment in the control arm will depend on the timing of relapse in relation to the end of adjuvant TMZ treatment (as part of the initial treatment with chemo-irradiation). Thus, this study will be developed as a three-arm study with the control arm being treated by either lomustine or TMZ depending on the timing of the relapse: (A) patients relapsing within 3 months from the end of adjuvant TMZ cycles (16 weeks from the first day of the last TMZ cycle) will receive lomustine; (B) patients relapsing three months or more after the end of TMZ chemotherapy (16 weeks from the first day of the last TMZ cycle) will receive TMZ standard dosing day 1-5 every 4 weeks.

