Arm 2: patients will be treated with ABT-414 monotherapy 1.0 mg/kg IV infusion over 30 to 40 minutes once every 2 weeks until one of the treatment withdrawal criteria has been met.

Arm 3: Patients in the control arm will be treated according to the timing of relapse.

Arm 3A: Patients relapsing during TMZ treatment or within the first 16 weeks after the first day of the last TMZ cycle will be treated with lomustine 110 mg/m² on day 1 of every 42-day treatment period.

Treatment will continue until one of the treatment withdrawal criteria has been met. Lomustine will be given for a maximum of one year.

Arm 3B: Patients relapsing 16 weeks or more after the first day of the last TMZ cycle will be treated with TMZ 150 mg/m² on day 1 to 5 for the first 28-day cycle, with dose escalation to 200 mg/m² in subsequent cycles in case of adequate tolerance. Treatment will continue until one of the treatment withdrawal criteria has been met.

[figure not shown]
Treatment should start within 96 hours from randomization.

Treatment at further progression will be according to investigators discretion. Day 1 of the first cycle will be the first day when the study medication is taken.

There will be an interim futility analysis organized. At interim analysis one or both of the ABT-414 arms might be discontinued based on lack of efficacy for PFS (Reject H1 in favor of H0) according to RANO criteria assessed by IRC (see section 8.3).

Disease will be assessed by study-specific MRI according to the study specific imaging protocol every 8 weeks. Response and progression will be assessed by the RANO criteria (see section 7.1).

The safety profile will be assessed separately for each cycle of therapy with CTCAE v4 (see section 7.2).

5 Therapeutic regimens, expected toxicity, dose modifications

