4.3 Randomization and Stratification

All subjects entered in the study will be centrally randomized at the EORTC Headquarters as described in Section 13.3 of the study protocol. The minimization technique used by the EORTC for random treatment allocation is based on the variance method with semi-random assignment dependent on a preset threshold as implemented by Freedman and White.¹ However, per suggestion of the ICH E9 statistical guidelines, the algorithm has been modified to incorporate a random allocation component in order to ensure an additional 15% of completely random assignments.

In this study, the threshold is set to 3, the total number of stratification factors.

Stratification factors are:

- Regions of the world (North America (USA, Puerto Rico & Canada) vs. Europe and Australia vs. Asia/other regions)
- WHO Performance Status (0 vs. > 0)
- Timing of relapse (< 16 weeks vs. ≥ 16 weeks after the first day of the last TMZ cycle)

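### Timing of relapse also fixes the control drug, so the Protocol 8.2.4 interaction test cannot be credited to timing alone, and the control-arm prognostic estimate mixes timing with drug

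*Protocol*

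**What the plan says.** Protocol 8.2.4 names three subgroup factors: timing of relapse (below 16 weeks, or 16 weeks and over, from the first day of the last TMZ cycle), MGMT promoter methylation, and EGFR pathway abnormality. Two analyses are planned for all three.

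- **Predictive value.** "To assess the predictive value of the above three factors for OS, PFS, NDFS, the score interaction test will be computed", from a Cox model with treatment, factor and their product. "For each interaction test, a significance of 10% will apply".
- **Univariate prognostic value.** Here "the score test will be computed by fitting a Cox model including the factor in each arm (control and treatments"), at an exploratory two-sided 5% level.

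The control drug is described in Protocol section 4 and again in SAP 4.2. Arm 3A covers early relapse: "Patients relapsing during TMZ treatment or within the first 16 weeks after the first day of the last TMZ cycle will be treated with lomustine". Arm 3B covers late relapse: "Patients relapsing 16 weeks or more after the first day of the last TMZ cycle will be treated with TMZ". The control-arm rationale in Protocol section 1.8 says the same: "the treatment in the control arm will depend on the timing of relapse in relation to the end of adjuvant TMZ treatment". The cut is also a stratification factor (Protocol 8.1.2, SAP 4.3).

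SAP 10.3 lists OS and PFS by timing of relapse. SAP 10.6 keeps the timing subgroup, with treatment-only Cox models, unstratified log-rank tests and forest plots. SAP 10.6 contains neither the interaction test nor the prognostic test, and the list of EORTC/AbbVie differences in SAP 12 does not add them. The protocol still plans both.

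**The concern.** Within Arm 3, timing of relapse and assigned drug are one variable. A treatment-by-timing interaction therefore compares the effect of ABT-414 against lomustine (early) with its effect against TMZ re-challenge (late). For Arm 1 the question itself changes: in late relapse both sides receive TMZ, so the contrast is an add-on comparison, while in early relapse it is not. A significant result could come from timing, from a difference between the two control drugs, or from both. A real timing effect could also be cancelled by a drug difference.

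The same applies to the prognostic model in the control arm, which sets early relapsers on lomustine against late relapsers on TMZ. Section 8.2.4 carries no caveat on either point. At stake is a wrong attribution in an exploratory result: a difference between comparators could be reported as timing predicting benefit, or a timing-plus-drug difference as prognosis.

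**Working it through.** **1. The plan's own figure.** The documents give no power for the interaction or prognostic tests. The design figure they do give reproduces: for 118 deaths, 1:1 allocation, HR 0.54 and one-sided 2.5%, Schoenfeld power is Φ(½·√118·|ln 0.54| − 1.96) = 91.7%, as in Protocol 8.1.1.

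**2. Can timing and control drug be separated?** Each comparison has four cells: control-early (lomustine), control-late (TMZ), treated-early and treated-late. An intercept, treatment, timing, treatment × timing and control drug make five parameters, but the design matrix has rank 4. Within Arm 3, an intercept, timing and drug make three parameters with rank 2. The drug effect is not estimable separately in either case, whatever the sample size.

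**3. Illustration for the interaction.**

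*From the documents:* 170 deaths in total and 118 per comparison (Protocol 8.1.1); HR 0.54; a 60/40 early/late split from historical data (Protocol 1.2).

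*Assumed:* deaths split 60/40 like patients; the 10% level is two-sided (not stated); ABT-414 has HR 0.54 against lomustine in both timing groups; TMZ v lomustine has HR *h* in both groups.

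- Deaths: control + treated = 118 and control + 2 × treated = 170, so treated = 52 and control = 66.
- Cells: control 39.6 and 26.4; treated 31.2 and 20.8.
- SE(interaction) = √(1/39.6 + 1/31.2 + 1/26.4 + 1/20.8) = 0.378.
- Early HR (v lomustine) = 0.54; late HR (v TMZ) = 0.54/*h*.
- Rejection = Φ(|ln *h*|/SE − 1.645) + Φ(−|ln *h*|/SE − 1.645).

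| *h* (assumed) | Early HR | Late HR | Abs(ln *h*)/SE | 10% test rejects |
|---|---|---|---|---|
| 1.0 | 0.54 | 0.54 | 0 | 10% |
| 0.9 | 0.54 | 0.60 | 0.28 | 11% |
| 0.75 | 0.54 | 0.72 | 0.76 | 20% |
| 0.6 | 0.54 | 0.90 | 1.35 | 39% |

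Values above 1 mirror these: *h* = 1/0.75 also gives 20%, with the interaction in the other direction.

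A Cox simulation (400 trials per scenario, 80 patients per arm, planned accrual, 31-month cut-off) used a different base: HR 0.54 against TMZ in both groups and a timing HR of 1.5. Lomustine/TMZ HRs of 0.67, 0.8, 1.0, 1.25 and 1.5 gave rejection in 28%, 16%, 9%, 15% and 28% of trials.

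**4. Control-arm prognostic estimate.** This model estimates the product of the timing HR (early v late) and the lomustine/TMZ HR. A timing effect is expected: Protocol 1.2 cites 12-month OS of 28% v 14% for late and early relapse in a study where all patients received TMZ. Under exponential survival that is ln 0.14/ln 0.28 = 1.54, so 1.5 is a reasonable illustration. With a true timing HR of 1.5, the simulated control-arm estimates were:

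| Lomustine/TMZ HR (assumed) | Control-arm 'prognostic' HR |
|---|---|
| 0.67 | 1.00 |
| 0.8 | 1.18 |
| 1.0 | 1.52 |
| 1.25 | 1.86 |
| 1.5 | 2.31 |

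Depending on the drug difference, the timing effect can vanish or be well overstated.

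**5. Where timing is not tied to drug.** In Arms 1 and 2 treatment does not depend on timing. With 52 deaths split 60/40, SE = √(1/31.2 + 1/20.8) = 0.283 per arm. Pooled over 104 deaths it is √(1/62.4 + 1/41.6) = 0.200. In control it is √(1/39.6 + 1/26.4) = 0.251.

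**The case against.** The control is timing-directed by design, and Protocol 1.8 says so. Randomisation is stratified on timing, so each subgroup contrast is a valid randomised comparison. The interaction validly asks whether benefit over the timing-directed control differs by timing; in the table above, 0.54 against 0.72 is a real difference on that definition. Section 8.2.4 calls the analyses exploratory and hypothesis generating, SAP 10.6 does not carry the two tests, and at *h* = 0.9 the rejection rate hardly moves from 10%. Separate prognostic models in Arms 1 and 2 are already planned. All of this stands, and it limits the point to attribution and labelling.

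Four stronger readings are tempting, and the documents do not support them:

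- *The control-arm test only compares lomustine with TMZ.* It does not: the patients also differ in timing, and Protocol 1.2 expects timing to matter. It isolates neither effect.
- *The interaction test is invalid.* Only its predictive label for timing fails.
- *The control-arm test mainly risks a false positive.* That presumes no timing effect; the protocol expects one, so the main problem is a biased estimate.
- *A misreading would decide who is considered for ABT-414.* Timing selects only the control drug. ABT-414 is given regardless of timing in Arms 1 and 2, and the protocol bars efficacy conclusions from exploratory results.

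What the objection does not remove is that 8.2.4 still names timing as a factor whose predictive value the test assesses, and no section warns that the comparator changes at the same cut.

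**Conclusion.** The point holds as a minor one. The aliasing follows from the design and needs no assumption. The timing interaction is a joint timing-and-comparator difference, and the control-arm timing estimate is timing and drug combined.

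The size depends on a TMZ v lomustine HR that the documents do not give and that could be 1.0 or lie on either side of it. Under the stated assumptions the 10% interaction test rejects in 10% to 39% of trials for ratios from 1.0 to 0.6, although the effect against lomustine is the same in both timing groups. The 60/40 split of deaths is also assumed; late relapsers are expected to live longer, so their share of deaths may be smaller.

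The confirmatory tests are unaffected: they compare each arm with the control as designed, and the log-rank test is stratified on timing.

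MGMT status carries a weaker form of the problem. Protocol 1.2 expects early relapsers to be mostly unmethylated and late relapsers mostly methylated, so MGMT partly tracks the control drug.

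**What to change.** 1. In Protocol 8.2.4, remove timing of relapse from the factors whose predictive value is assessed. Report its interaction as heterogeneity against a stratum-specific control. In 8.2.4, SAP 10.3 and SAP 10.6, label the timing subgroups, including the forest plots, *v lomustine* and *v TMZ re-challenge*.
2. Base the prognostic value of timing on Arms 1 and 2, reported separately. A pooled, arm-stratified estimate may be added if the arms agree; it should not replace the separate ones, because Arm 1 gives TMZ to everyone and the effect of TMZ may itself vary with timing. Label the control-arm result *3A lomustine v 3B TMZ: timing and drug combined*.
3. State that the MGMT interaction and control-arm prognostic results are partly confounded with control drug.

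The cost is wording and a small change to an exploratory analysis. No new data are needed and no confirmatory test changes. The per-arm estimates for timing are less precise (SE about 0.28 per arm, against 0.25 in control), but they are not mixed with a change of drug.
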